6.7. Safety Analyses

Safety analyses will be performed on the FAS. The analysis of solicited and unsolicited AEs will be restricted to the Safety Subset, whereas for the analysis of serious AEs (SAEs), Covid cases, potential adverse events of special interest (AESI) and potential AESI qualified for assessment the entire FAS population will be used. Solicited and unsolicited AEs accidentally captured for participants outside the Safety Subset of the main cohort, will be listed.

Continuous variables will be summarized using the following statistics, as appropriate: number of observations, median, minimum and maximum. Frequencies and percentages will be generated for categorical variables. No formal comparisons between groups will be provided.

Safety data will be analyzed by vaccine regimens, by risk level and by age category (<75 years and ≥ 75 years) for the first and second year and over the whole study. Safety data may also be analyzed per country. For unsolicited AE, denominator for the percentages is the number of participants in the considered population and phase (or interval) for a certain regimen (incidence per 100 participants/phase) risk level and age category. For solicited AEs, the denominator for the percentages is the number of participants with data assessed by the PI in the considered population and phase for a certain regimen (incidence per 100 participants/phase), risk level and age category.

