Humoral immunity sample, mL	● ^x 20	● ^x 20		● 20	● 20		● ^x 20	● ^x 20	
Cellular immunity sample, mL	● 40	● 40		● 40	● 40		● 40	● 40	
Nasosorption sample (SAM)	●	●					●		
SAFETY SUBSET ONLY:									
Thermometer training and distribution	●								
Ruler training and distribution	●								
Solicited AE recording ^y	●								
Unsolicited AE recording ^z	Continuous								
Concomitant medications	Continuous								
Vital signs ^{aa}	● ●								
eDiary review of solicited AEs by study staff		●							
Blood Draw Volumes: IMMUNO SUBSET PARTICIPANTS									
Approx. daily blood draw, mL	62	62		60	60		62	60	
Approx. cumulative blood draw, mL	62	124	124	184	244	244	306	366	366
Blood Draw Volumes: NON-IMMUNO SUBSET PARTICIPANTS									
Approx. daily blood draw, mL	17	17					17		
Approx. cumulative blood draw, mL	17	34	34	34	34	34	51	51	51

1 pre-dose

Note: At any clinic visit, an abbreviated, symptom directed physical examination may be performed if deemed necessary by the investigator based on any clinically relevant issues, clinically relevant symptoms, and medical history.

Footnotes:

- a. For Immuno Subset participants, where the timing of the 24-week post-vaccination visits and end of first RSV season or Month 6 (Day 182) visits may overlap, procedures can be combined.
- b. For the Northern Hemisphere (NH), the end of the first RSV season is defined as 15 April 2022. For the Southern Hemisphere (SH), the end of the first RSV season is defined as 30 September 2022. This visit (Visit 3) is then referred to as “End of first RSV season” visit. End of first RSV season procedures may be conducted on the same day as Visit 1, or before Visits 2, 2a, 2b, and 2c depending on the date of enrollment of the participant. If a participant is enrolled after the maximum window of the “End of first RSV season” visit (ie, after 29 Apr 2022 for NH and after 14 Oct 2022 for SH), only a “Month 6” (182 days, -7/+14 days post vaccination) safety follow-up call is required to collect information on SAEs and potential AESIs.

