
 To demonstrate the efficacy of active study vaccine in the prevention of predefined clinically relevant disease associated with RT-PCR-confirmed RSV-mediated ARI over the whole study when compared to placebo 	
 First occurrence of predefined clinically relevant disease associated with RT-PCR-confirmed RSV-mediated ARI over the whole study with onset at least 14 days after dosing of study vaccine
NON-CONFIRMATORY SECONDARY	

 To evaluate safety in terms of serious adverse events (SAEs) and adverse events of special interest (AESIs) until 6 months after vaccination 	
 Occurrence and relationship of vaccination to SAEs and AESIs until 6 months after vaccination

 In the Safety Subset and in subgroups of the Safety Subset (including but not limited to participants at increased risk of severe RSV disease), to evaluate the safety and reactogenicity in terms of solicited local and systemic adverse events (AEs) during 7 days after vaccination, and in terms of unsolicited AEs during 28 days after vaccination 	
 Occurrence, intensity, duration and relationship to vaccination of solicited local and systemic AEs during 7 days after vaccination and of unsolicited AEs during 28 days after vaccination

 In the Immuno Subset and in subgroups of the Immuno Subset (including but not limited to participants at increased risk of severe RSV disease), to evaluate the immunogenicity of active study vaccine when compared to placebo 	
 Characterization of the humoral and cellular immune responses in the Immuno Subset with emphasis on neutralizing and binding antibodies and antigen-specific cytokine production by T-cells

Objectives	Endpoints

 To assess the reduction of symptom severity in participants with an RT-PCR-confirmed RSV-mediated ARI when compared to placebo over the whole study 	
 In participants with an RT-PCR-confirmed RSV-mediated ARI over the whole study: the area under the curve (AUC) of the change from baseline in Respiratory Infection Intensity and Impact Questionnaire (RiiQ^a) Total Symptom score
EXPLORATORY	

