9.5. Planned Analyses

9.5.1. Analysis Plan for the Interim and Primary Efficacy Analyses

The following describes the analysis plan for the interim analysis and the primary analysis. This takes into account participants enrolled in the Global cohort. Any local cohort enrolment beyond the Global cohort will be analyzed separately, except if individual participant enrollment started before the database cut-off of the primary analysis.

The interim analysis plan is as follows:

- Based on a database cut-off date of 15 September 2022, an IA by IDMC will be performed. The IDMC will evaluate in an unblinded fashion if the LL of the $(100-2 \times \alpha_1)\%$ 2-sided CI around the VE (1-relative risk rate) is above 20% and additionally a point-estimate of VE >50% is observed for Group 1. If the success criteria are met, the sponsor will be notified. The database used for the IDMC analysis will be unblinded for the sponsor and the primary analysis will be performed by the sponsor at the same significance level (α_1). If the success criteria are not met, the participants will be followed further, and the same steps will be performed at the following subsequent database cut-offs:
- 24 October 2022 with an alpha level α_2
- 22 January 2023 with an alpha level α_3

- Provided no primary analysis occurred earlier, the primary analysis will be performed with database cut-off 30 April 2023 with alpha level α_4

Figure 3 displays the interim and primary analysis plan.

If VE is not demonstrated to be significantly >20% with a point estimate >50% at the time of the primary analysis, the study will be stopped.

[figure not shown]
The total alpha will be controlled at 2.5%. A Pocock-like alpha spending function as described by DeMets (DeMets 1994) with a target number of events of 76 used to spend the alpha over the different analyses. The different alphas to be used during every IA are shown above in Figure 3 and the calculations are explained below in Table 9.

Table 9: Alpha-spending at the Prespecified Analysis Timepoints

Alpha	Description of how to obtain alpha
α_1	Alpha obtained from Pocock-like alpha spending function with information fractions = [# RSV LRTD events by 15 September 2022 / 76 [‡] , 1]
α_2	Alpha obtained from Pocock-like alpha spending function with information fractions = [# RSV LRTD events by 15 September 2022 / 76 [‡] , # RSV LRTD events by 24 October 2022 / 76 [‡] , 1]

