α_3	Alpha obtained from Pocock-like alpha spending function with information fractions = [# RSV LRTD events by 15 September 2022 / 76 [‡] , # RSV LRTD events by 24 October 2022 / 76 [‡] , # RSV LRTD events by 22 Jan 2023 / 76 [‡] , 1]
α_4	Alpha obtained from the remaining alpha to be spent (2.5% - total alpha spent during the interim analyses) and the actual information fractions observed at all analyses. That is, the information fraction, IF = [# RSV LRTD events by 15 September 2022 / # RSV LRTD events by 30 April 2023, # RSV LRTD events by 24 October 2022 / # RSV LRTD events by 30 April 2023, # RSV LRTD events by 22 January 2023 / # RSV LRTD events by 30 April 2023, 1]. The final alpha will be calculated using the user-defined alpha spending function approach (Jennison 2000).

[‡]76 target sample size for 90% power with 65% VE. Note that if at any of the interim analyses 76 or more RSV LRTD events have been observed, all remaining alpha will be spent and no further (interim) analyses for primary efficacy endpoint will be performed.

At the time of the primary analysis, unblinded safety and efficacy data will be analyzed. Immunogenicity data will be included if available.

Figure 3: Interim and Primary Analysis Plan

For the first interim analysis, ARIs with an onset up to 1 September 2022 will be included and a database cut-off of 15 September 2022 will be used. For the second IA, ARIs with an onset up to 10 October 2022 will be included and a database cut-off of 24 October 2022 will be used. For the third IA, ARIs with an onset up to 8 January 2023 will be included and a database cut-off of 22 January 2023 will be used. For the primary analysis, ARIs with an onset up to 15 April 2023 will be included and a database cut-off of 30 April 2023 will be used.

DB= database, IA= interim analysis, IDMC = independent data monitoring committee, PA=primary analysis, PPE=Per-protocol Efficacy, POS= positive

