5. PLANNED ANALYSIS

5.1. Analysis Plan for the Interim and Primary Analysis

Figure 1 displays the interim and primary analysis plan.

Figure 1: Interim and Primary Analysis Plan

For the first interim analysis, ARIs with an onset up to 1 September 2022 will be included and a database cut-off of 15 September 2022 will be used. For the second IA, ARIs with an onset up to 10 October 2022 will be included and a database cut-off of 24 October 2022 will be used. For the third IA, ARIs with an onset up to 8 January 2023 will be included and a database cut-off of 22 January 2023 will be used. For the primary analysis, ARIs with an onset up to 15 April 2023 will be included and a database cut-off of 30 April 2023 will be used.

DB= database, IA= interim analysis, IDMC = independent data monitoring committee, PA=primary analysis, PPE=Per-protocol Efficacy, POS= positive

Please refer to Section 9.5.1 in the CTP for more details on the timing of the Interim and Primary analysis. Information regarding additional country-specific enrollment, beyond the global cohort enrollment, can be found in the country specific amendments.

In case the analysis is conducted prior to the completion of the study recruitment, all participants recruited in the global and local cohorts up to the database cut off will be used in the efficacy analysis, regardless the number of events already observed in the different local cohorts. Moreover, only participants vaccinated >14 days prior to the database cut off will be taken into account for the analysis of the primary efficacy endpoint, including the counting of LRTD cases. For the sensitivity analysis based on the FAS all participants will be taken into account.

Note: Participants with an RT-PCR-confirmed RSV-mediated ARI with onset within 14 days after vaccination, participants who discontinue within 14 days after vaccination and participants that have not reached 14 days (inclusive) after vaccination, will be excluded from the PPE population and thus from the counting of the number of events.

Local study teams will be blinded to study vaccination until the primary analysis as specified per local requirements. The local cohorts' primary analysis cannot be conducted prior to the primary analysis of the global cohort.

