6.7.1.1.4. Missing Data

Missing data (grade, relationship) will not be imputed. Participants who do not report an event will be considered as participants without an event. An AE with a missing severity or relationship will be considered as an AE reported but will be considered as not reported for the severity or relationship. For example, an AE with missing severity will be considered as an AE reported for the analysis of any grade but will be considered as not reported for the analysis of at least grade 3. The analysis of solicited AEs will include the safety data as documented by the investigator.

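### If an early cut-off triggers the primary analysis, crude SAE and AESI percentages in the pooled 0-6-month and phase rows would understate the absolute 6-month risk, because participants still short of 6 months stay in the denominator

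*SAP*

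**What the plan says.** - **Endpoint.** Protocol 3 lists a non-confirmatory secondary endpoint with a fixed window: "Occurrence and relationship of vaccination to SAEs and AESIs until 6 months after vaccination".
- **Timing.** Protocol 9.5.1: "Based on a database cut-off date of 15 September 2022, an IA by IDMC will be performed". If the criteria are met, that database is unblinded to the sponsor and "the primary analysis will be performed by the sponsor at the same significance level". The same steps apply at 24 October 2022 and 22 January 2023; otherwise the cut-off is 30 April 2023.
- **Content.** Protocol 9.5.1: "At the time of the primary analysis, unblinded safety and efficacy data will be analyzed".
- **Incomplete follow-up is foreseen.** Protocol 4.1 says what happens if the primary outcome is negative and some participants have not completed 6 months. SAP 5.1 has a rule beginning "In case the analysis is conducted prior to the completion of the study recruitment". Footnote b of Protocol 1.3.1 provides for enrolment "after 29 Apr 2022 for NH and after 14 Oct 2022 for SH".
- **Summary measure.** SAP 6.7.1.1.2 tabulates number and percentage of participants. In SAP 6.7 the "denominator for the percentages is the number of participants in the considered population and phase (or interval") for a regimen. SAP 6.7.1.1.4 adds: "Participants who do not report an event will be considered as participants without an event".
- **Truncation.** SAP Tables 4 and 5 end each phase or interval at the earliest of last contact, database cut-off or nominal end. Table 5 also defines a pooled 0-6-month interval. Its nominal end is vaccination plus 169 days, or the Day 169 visit if later, whereas the Month 6 contact in Protocol 1.3.1 is Day 182.

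**The concern.** A participant vaccinated three months before the cut-off has been observed for about half of the 6-month window, yet counts as one full participant in the pooled 0-6-month row and, with no event reported so far, as event-free. The resulting percentage mixes follow-up lengths and no longer estimates a 6-month risk. The efficacy model in SAP 6.3.3 handles the same problem with a follow-up-time offset; the safety tables have no counterpart.

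The safety analysis is purely descriptive, so the absolute percentages are its main product. An early primary analysis could report SAE, fatal AE and AESI percentages that are too low, that depend on which cut-off triggered it, and that are not comparable with later tables or with the precision figures in Protocol 9.2.3.

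**Working it through.** **1. The plan's own figures.** Protocol Table 7 uses 1 − (1 − p)^N. For N = 15,340 and p = 0.01%, this gives 78.4% (stated 78%). The one-sided zero-event bound 1 − 0.05^(1/N) is 0.0195%, consistent with the stated figure of below 0.025%. Both treat every active participant as fully observed.

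**2. Who can be incomplete.** Counting back from each cut-off, anyone vaccinated after these dates is short of the window (the SAP's numbering of vaccination as Day 1 moves the Day 182 dates one day later):

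| Cut-off | 182 days back | 169 days back |
|---|---|---|
| 15 Sep 2022 | 17 Mar 2022 | 30 Mar 2022 |
| 24 Oct 2022 | 25 Apr 2022 | 8 May 2022 |
| 22 Jan 2023 | 24 Jul 2022 | 6 Aug 2022 |

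A Northern Hemisphere participant enrolled after 29 April 2022 completes 182 days only after 28 October 2022, so is incomplete at both of the first two cut-offs. The Southern Hemisphere date, 14 October 2022, falls after the first cut-off and says nothing about that dataset.

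**3. Size of the shortfall.** Let f be the share short of 182 days. The documents do not give f, so it is varied. Assume that follow-up in that share is uniform over 0-182 days.

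- Pooled row, constant hazard: the incomplete group shows on average half its risk, so crude/true ≈ 1 − f/2.
- Pooled row, all events spread over the first 28 days: the incomplete group misses 14/182 of its events, so crude/true = 1 − f × 14/182.
- Row for 57 days to 6 months, own denominator, constant hazard (taking 56 to 182 days): entrants are (1 − f) + f × 126/182. Expected events, as a fraction of the full 6-month risk, are (1 − f) × 126/182 + f × (126/182) × 63/182. At f = 25%: 0.579/0.923, divided by 0.692, = 0.906.

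| f | Pooled, constant hazard | True 2.0% shown as | Pooled, first 28 days | 57 days to 6 months row |
|---|---|---|---|---|
| 5% | 0.975 | 1.95% | 0.996 | 0.982 |
| 10% | 0.95 | 1.90% | 0.992 | 0.964 |
| 25% | 0.875 | 1.75% | 0.981 | 0.906 |
| 50% | 0.75 | 1.50% | 0.962 | 0.795 |

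The 2.0% risk is illustrative only.

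**4. Effect on the precision figures.** For rare events under a constant hazard, the effective N is about 15,340 × (1 − f/2). At f = 10%, 25% and 50% this is 14,573, 13,422 and 11,505. The 78% becomes 76.7%, 73.9% and 68.4%; the zero-event bound becomes 0.0206%, 0.0223% and 0.0260%. Only the last exceeds the stated 0.025%.

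**5. Between-arm ratio.** With the same f in both arms, equal risks give a ratio of 1.000, and true risks of 4% versus 2% give 2.002 at f = 50% instead of 2.000.

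**6. Window.** Table 5 closes 182 − 169 = 13 days before the Month 6 contact day. The Day 169 visit is for the Immuno Subset only, so for everyone else the interval ends at vaccination plus 169 days. A later event that is still inside the endpoint as scheduled would fall in the row for beyond 6 months.

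**The case against.** - **The denominator sentence is about unsolicited AEs and is specific to the phase or interval.** Correct on both counts. Its use for SAEs and AESIs is an inference, though a firm one: the only intervals defined are those of Table 5, written for AESIs and extended to SAEs in SAP 6.10.2, and SAEs sit in the unsolicited AE summary. A reader might infer that incomplete participants count fully in every row. They do not: someone who never reached the 57-day interval is not in its denominator. That row is still diluted, but less.
- **Open recruitment is only a contingency.** This stands. A reader might infer that recruitment was open at 15 September 2022, or attach a definite incomplete share by assuming an accrual calendar. SAP 5.1 and footnote b are conditional, and neither document gives an accrual curve or closing date.
- **The problem clears itself.** Largely true. After a negative primary result the study continues until all have 6 months, safety is analysed again at study end, and SAP 6.11 has all participants followed for 6 months after termination. SAP 4.0 also postdates every cut-off. But SAP 6.11 limits final safety output to Table 4 periods, so it promises no 0-6-month percentage to replace an earlier one.
- **Events may come early.** Protocol 2.2 puts onset of vaccine-induced TTS symptoms at about 1 to 2 weeks, which favours the small-shortfall column for that AESI. Background SAEs need not follow that pattern.
- **Follow-up is already summarised (SAP 6.2).** That gives context, but does not correct the percentages or count those who completed 6 months.

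**Conclusion.** The point holds as a limited one. At any safety analysis made before all participants have 6 months of follow-up, the pooled 0-6-month and phase-level SAE and AESI percentages understate absolute risk. The size cannot be derived from the documents. Under a constant hazard and uniform partial follow-up it is about f/2 in relative terms; with events confined to the first 28 days it is below 4% for f up to 50%.

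Two stronger readings are not supported. One is that the vaccine-placebo comparison is biased: randomisation is parallel at 2:1, both arms are truncated alike, and the ratio barely moves. The other is that the final safety results are understated too: with 6 months of follow-up for all, no cut-off shortfall remains apart from dropouts. The change is worth making because it is cheap and the percentages are the main safety output, not because a conclusion would reverse.

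**What to change.** In SAP 6.7, for any safety analysis made before all participants have 6 months of follow-up, add by arm for SAEs, fatal AEs and AESIs:

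- exposure-adjusted incidence (participants with an event per 100 person-years, time ending at the earliest of event, end of the 6-month window, last contact or cut-off) with 95% CI;
- Kaplan-Meier cumulative incidence at 6 months;
- the number of participants who have completed 6 months, beside the crude counts.

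Keep the crude percentages as supportive. Reconcile Table 5 (Day 169) with the Month 6 contact (Day 182) so that one window defines the endpoint in all tables. Where a report from an early cut-off already exists, supply these tables or state the limitation.

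The cost is SAP wording and a few tables. No new data are needed, since vaccination, event, last-contact and cut-off dates are already available. Reported absolute rates would be slightly higher.

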6.7.1. Adverse Events

6.7.1.1.1. Definitions

Solicited AEs shown in the tables are extracted from the investigator assessment pages (CE) of the CRF. For unsolicited AEs, only the AEs within the 28-day period following vaccination will be presented in the safety tables except for SAE, Covid cases and potential adverse events of special interest, which will be captured and tabulated in the outputs covering the whole study period. Unsolicited non-serious adverse events collected outside the 28-day period following a vaccination will be presented through listings.

Solicited administration site symptoms will be by definition considered as related to the study vaccine.

The severity of the AEs will be classified as grade 1 to 4. Solicited events of grade 0, not reported in the CE domain, will therefore not be reported in the AE analysis

Any ARI recorded as an (S)AE in the eCRF will be excluded from any AE analysis if it is a confirmed RSV infection by RT-PCR (nasal swabs and sputum sample, when available) based on the laboratory or if it is connected with a hospitalized confirmed RSV infection based on an FDA-approved RT-PCR test at the local laboratory. RT-PCR confirmed RSV-mediated ARIs are part of the efficacy evaluation and will be summarized separately from the safety.

For AESI analyses, the following subcategories are defined:

- Potential AESIs as identified by the investigator in the database
- Potential AESIs selected programmatically

Those include all reported AEs that are identified by the selection rule:

- SMQ (Standardised MedDRA Queries) = “EMBOLIC AND THROMBOTIC EVENTS (SMQ)”
or
- (SUB_SMQ1 = “HAEMATOPOIETIC THROMBOCYTOPENIA (SMQ)” and SCOPE in (“BROAD”, “NARROW“)) or HLT (higher level term)=“Thrombocytopenias”
- Potential AESIs qualified for assessment
Potential AESIs (programmed/CRF) that have risk levels assessed by one of the following three criteria are considered 'qualified for assessment':
 - Brighton Collaboration Level (Level 1-5)
 - CDC Tier (non-tier 1/ 2, tier 1, tier 2)
 - PRAC criteria (confirmed, possible, probable, unlikely, criteria not met)

